## 2 INTRODUCTION: BACKGROUND INFORMATION AND SCIENTIFIC RATIONALE

### 2.1 Background Information

Acne Vulgaris (AV), hereinafter referred to as acne, affects up to 50 million Americans and is the most common skin condition in the United States (US) (Bickers et al, 2006). Acne affects both adolescents and young adults. Approximately 85 percent of people between the ages of 12 and 24 experience at least minor acne (Bhate & Williams, 2013). Since patients may have acne over a long duration of time, and may also experience recurrence and relapse, and manifestations such as acute outbreaks or slow onset, acne may be classified as a chronic disease (Cherynshov et al, 2018).

Core outcomes in acne studies often focus on clinical assessment of acne severity, in terms of investigator global assessment (IGA) or lesion counts. Patient reported outcome measures (PROMs) have been sporadically used, but the increased recognition of their importance to patients has resulted in a proliferation of studies depicting the impact of acne on patient's health-related QoL (HRQoL) (Thiboutot et al, 2019). Acne has been shown to negatively affect QoL resulting in low self-esteem, increased social and emotional anxiety (Timms, 2013; Revol et al, 2015). Patients with acne report more effects of their skin condition on their functioning, emotions, and symptoms than do patients with isolated benign skin lesions or those in the normative sample (Lasek & Chren, 1998). Acne has been associated with considerable psychosocial impact, causing significant negative effects on self-image leading to feelings of isolation and loneliness, and a significantly lower self-attitude, uselessness feeling, sense of pride and self-worth, and body satisfaction (Gieler, 2015).

Several QoL instruments have been used in acne studies, with varying level of focus on patient attributes impacted by acne (Alexis et al, 2014; Cherynshov et al, 2018). An expert panel of dermatologists was recently convened (in December 2020) to review the existing QoL instruments and identify key patient-centric elements that reflects the day-to-day concerns of their adult and pediatric acne patients. An existing 17-item validated instrument, namely, Acne Symptom and Impact Scale (ASIS) that asks patients about the acne signs and impact of acne on emotional and social wellbeing, was used as the anchor for further panel deliberations on

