## 7 STUDY SCHEDULE & PROCEDURES

Study eligible patients who are considered as candidates for sarecycline treatment as part of usual care Acne management will be screened, consented and recruited into the study, followed for up to 12 weeks post-index date, encompassing four distinct data collection encounters. With 'T' being the index date of sarecycline treatment initiation, the baseline data collection may transpire anytime between T= -2 weeks post-index date and T= +4 days post-index date; the 4-week follow-up data collection will happen at T=4 weeks post-index date  $\pm$  4 days; the 8-week follow-up data collection will happen at T=8 weeks post-index date  $\pm$  4 days, and 12-week follow-up data collection will happen at T=12 weeks post-index date  $\pm$  4 days. Index date is the date of initiation of sarecycline treatment, when the subject took the first sarecycline dose.

Different data elements will be collected from Site Investigators and from study Subjects at these data collection encounters, as outlined below. For patients of age 12yrs and older, acne patients themselves will complete relevant PRO elements pertinent to study endpoints, at all encounters; for patients of age 9-11yrs, parents/caregivers of pediatric patients will complete the PRO elements at all encounters, serving as a proxy, upon consulting with their child on question responses.

The schedule of events is summarized in Appendix A.

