patients reporting “Quite a bit/Very” at Week-12, to compute respective P values. Continuous measures will be assessed using summary statistics; paired sample t-tests will be used to assess statistical differences for CFB evaluations, while independent sample t-tests will be used to assess statistical differences between different patient groups (for subgroup analysis) for a given measure at a particular timepoint (such as Baseline or Week-12).

Computation of statistical differences will be performed only as an exploratory step (and not for hypothesis testing), considering the descriptive nature of the study; for such exploratory evaluation, P value  $\leq 0.05$  will be considered significant. All statistical analyses will be based on all available data assuming that all missing data are uninformative and will be conducted using appropriate statistical software, such as SAS.

An interim analysis will be conducted using FAS, upon completion of 12 weeks of data collection (from both patients and clinicians) for ~200 study Subjects, using the statistical methods identical to the analyses planned for FAS-based final data analyses; the focus of the interim analyses will be the primary objective, secondary objective and select additional objectives, as outlined below; no subgroup analyses will be considered.

- FAS cohort demographics
- PROs: Antibiotic attitudes at baseline
- PROs: CFB in EPQ measures
- PROs: CFB in ASIS measures
- PROs: CFB in Patient Acne Severity and How Face Looks (with and without LOCF imputation)
- PROs: CFB in Parent/caregiver concerns about the child with Acne:
  - Understanding child's concerns
  - Concerned about child's acne
  - Concerned about child's ability to accomplish future goals
- Facial IGA and Facial IGA success (with and without LOCF imputation)
- Select comparison of patient and clinician reported measures: Acne Severity (with LOCF imputation)

- Select comparison of pediatric patient and caregiver reported measures:
  - Understanding child's concerns
  - Concerned about child's acne
  - Concerned about child's ability to accomplish future goals
- Clinician satisfaction with sarecycline
- Sarecycline treatment characteristics

The description of the individual study measures are outlined in the forthcoming sections.

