#### **6.6.3 Comparison of Investigator and Subject Assessment of AV Severity**

The IGA and Subject perception of AV severity at Week 12 will be compared and reported using descriptive statistics, to portray the level of concordance/discordance in stakeholder perceptions. This analysis will be conducted for the entire cohort and for select subgroups outlined in Section 6.3.2. Correspondingly, the Investigator and Subject responses to the questions related to AV severity at baseline will also be compared and reported using descriptive statistics.

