### 7.3 Tables for comparison of patient and clinician data

For tables comparing patient and clinician data, the FAS dataset is used for analysis only in the instances patient data has corresponding clinician week 12 data. All data tables in this section pertain to FAS population.

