## 12.2 Appendix B: Select Study Questionnaires

### ASIS

Please read and answer each of the following questions about **acne signs and symptoms**. Before answering each question, **look in the mirror and think about the acne on your face**. Select one answer for each question that best describes your experience with acne **right now**. There are no right or wrong answers.

1. How oily is your face right now?

Not at all	A little	Somewhat	Quite a bit	Very
				

2. How many pimples do you have on your face right now?

None	A few	Some	Quite a bit	A lot
				

3. How many acne scars (holes or indents) do you have on your face right now?

None	A few	Some	Quite a bit	A lot
				

4. How many scabs from acne do you have on your face right now?

None	A few	Some	Quite a bit	A lot
				

5. How many dark marks from acne do you have on your face right now?

None	A few	Some	Quite a bit	A lot
				

6. How many blackheads do you have on your face right now?

None	A few	Some	Quite a bit	A lot
				

7. How many whiteheads do you have on your face right now?

None	A few	Some	Quite a bit	A lot
				

8. How much redness do you have on your face right now?

None	A few	Some	Quite a bit	A lot
				

9. Overall, how is the acne on your face right now?

Clear	Almost clear	Mild	Moderate	Severe
				

Please read and answer each of the following questions about how **acne impact your quality of life**. Before answering each question, look in the mirror and think about the acne on your face. Select one answer for each question that best describes your experience with acne in the past 7 days. There are no right or wrong answers.

10. Over the past 7 days, rate how your face looked because of your acne.

Excellent	Very good	Good	Fair	Bad
				

11. Over the past 7 days, how often did you feel sad because of the acne on your face?

Never	Rarely	Some of the time	Most of the time	All of the time
				

12. Over the past 7 days, how often did you feel embarrassed because of the acne on your face?

Never	Rarely	Some of the time	Most of the time	All of the time
				

13. Over the past 7 days, how often did you feel self-conscious because of the acne on your face?

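### The SAP specifies the patient–clinician severity comparison only with LOCF, so the Week 4 and Week 8 columns can set a current rating beside an out-of-date one

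*SAP*

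**What the plan says.** The comparison is an additional objective. SAP 6.6.3 compares the IGA with the patient's own severity rating at Week 12 and at baseline, descriptively, "to portray the level of concordance/discordance in stakeholder perceptions". It does not mention imputation.

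The interim list in SAP 6.3.1 includes "Select comparison of patient and clinician reported measures: Acne Severity (with LOCF imputation"). In the same list, the bullets for the patient severity and appearance items and for the IGA ask for results both with and without LOCF. This bullet asks for LOCF only. The interim is to be run "using the statistical methods identical to the analyses planned for FAS-based final data analyses", so the bullet also bears on the final analysis.

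SAP 6.9 applies LOCF to the IGA and to ASIS items 9 and 10 at Week 12, and also at Weeks 4 and 8. Tables 7.3.1–7.3.4 show patient and clinician severity at baseline and Weeks 4, 8 and 12, with available-data denominators. Their titles do not mention LOCF, although the tables in 7.1 and 7.2 that use it say so in theirs. The introduction to SAP 7.3 adds that "the FAS dataset is used for analysis only in the instances patient data has corresponding clinician week 12 data".

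The patient item reads "Overall, how is the acne on your face right now". The clinician item in Table 7.2.4.1 asks about the same moment.

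**The concern.** A comparison of perceptions presumes that both raters are judging the same acne. Protocol 2.1 describes a disease in which patients "may also experience recurrence and relapse, and manifestations such as acute outbreaks or slow onset", and it cites two pivotal trials with benefit after 12 weeks of treatment. A score carried forward from an earlier encounter is therefore a rating of different acne, and on average of worse acne if the patient is improving. Set beside the other rater's current score, it appears as a difference in perception when it is a difference in date.

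The passages also cannot all be followed. The interim bullet calls for LOCF, the named analysis and its tables are silent, 6.9 supplies a general LOCF rule that covers both items, and 7.3 restricts the tables by the presence of Week 12 clinician data. Two programmers could produce different tables from the same data and each claim to follow the SAP.

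**Working it through.** The documents give no sample size, power or agreement figure for this comparison, so there is no stated number to reproduce. The check is what LOCF can fill, how old the filled value is, and what that does to the planned tables.

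**1. What can be filled at Week 12.** SAP 6.2 and Section 7 make the FAS in essence the Week 12 survey completers, and Section 7 takes their PRO items as complete. The patient's Week 12 rating is then present. SAP 7.3 requires the clinician's Week 12 data. Ratings left for LOCF at Week 12: essentially 0 of about 200 at the interim.

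**2. What can be filled at Weeks 4 and 8.** Neither the FAS definition nor the 7.3 restriction requires data at these encounters. SAP 6.10 expects missed visits and does not count them as deviations. Either rater's score may be missing and so carried forward. A missing Week 4 IGA takes the baseline value, which eligibility fixes at 3 or 4 and which can therefore never be clear or almost clear.

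**3. Age of the carried value** (windows from Protocol 7: ±4 days at follow-up, −14 to +4 days at baseline).
- Week 4 carried to Week 8: nominal 28 days, range 28 − 8 = 20 to 28 + 8 = 36.
- Baseline carried to Week 4: nominal 28 days, range 24 − 4 = 20 to 32 + 14 = 46.
- Baseline carried to Week 8: nominal 56 days, range 52 − 4 = 48 to 60 + 14 = 74.

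**4. Effect on the planned tables.** Let f be the fraction of one rater's scores carried forward and Δ the rise in clear/almost clear over the carried interval. That rater's percentage is lowered by f × Δ. With Δ = 20 points in 4 weeks (assumed):
- f = 5%: 0.05 × 20 = 1 point
- f = 10%: 0.10 × 20 = 2 points
- f = 15%: 0.15 × 20 = 3 points

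If both raters have carried values and the same Δ, the difference between them is distorted by (f for one − f for the other) × Δ, which is smaller.

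**5. Different rating days within one window.** No passage requires same-day ratings. The largest possible gap is 4 + 4 = 8 days at follow-up and 14 + 4 = 18 days at baseline. Take two raters who would agree perfectly on the same day, five equally frequent categories, and a symmetric one-category move with probability q between the two days; moves beyond either end of the scale are blocked. Exact agreement is 1 − 0.8q:

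| q | Exact agreement | Clear/almost clear, each rater |
|---|---|---|
| 5% | 96% | 40% |
| 10% | 92% | 40% |
| 20% | 84% | 40% |
| 30% | 76% | 40% |

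Tables 7.3.1–7.3.4 show each rater's distribution side by side, with no cross-tabulation or kappa. Symmetric fluctuation therefore leaves them unchanged. Only a systematic gap would show. With the same assumed 20-point rise over 28 days, gaps of 2, 4 and 8 days shift one rater by 20 × 2/28 = 1.4, 20 × 4/28 = 2.9 and 20 × 8/28 = 5.7 points.

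**The case against.** The strongest reply is that the SAP already protects its named timepoint. The 7.3 restriction excludes patients without clinician Week 12 data, FAS membership supplies the patient's rating, and the interim itself is triggered "upon completion of 12 weeks of data collection (from both patients and clinicians) for ~200 study Subjects". A reader might infer from the LOCF bullet that investigators will look harsher than patients at Week 12, or that some percentage of Week 12 pairs becomes false disagreement. The documents do not support either while 7.3 applies. Such a percentage would also describe a per-patient statistic that the SAP does not plan. The exposure exists at Week 12 only if the interim bullet is read as overriding 7.3. In that case the clinician's score would be the one carried, from nominally 28, 56 or 84 days earlier.

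A reader might also infer that flares between unequal rating days will be counted as rater disagreement at every visit, given that "the baseline data collection may transpire anytime between T= -2 weeks post-index date and T= +4 days post-index date". The planned tables do not support that, because symmetric change cancels in them. Appendix A places both ratings at the same encounter. Encounters at baseline and Week 12 are expected to be clinic visits, and SAP 5.3.1 reports that the IGAs at those two visits were done in person. The 8 and 18 days are outer limits, and nothing shows a systematic gap.

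Finally, the comparison is descriptive, and its p-values, if any, are exploratory. All of this stands. It does not reach the Week 4 and Week 8 columns, where LOCF can operate and 7.3 gives no protection, nor the mismatch between the passages.

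**Conclusion.** The point holds for Weeks 4 and 8, and as an inconsistency to be resolved. Followed as written, the LOCF bullet puts scores that are nominally 28 or more days old beside current ones. If acne is improving, this moves the carried-forward rater's distribution toward greater severity. Which rater that is depends on whose ratings are missing more often.

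The size is about 1–3 percentage points in clear/almost clear. That rests on three assumptions that the documents do not supply: 5–15% of one rater's scores carried forward, few or none of the other's, and a 20-point rise in 4 weeks. Week 12 is essentially unaffected under 7.3, and the primary and secondary endpoints are untouched. The impact is limited, but imputation adds nothing to a question about how two people see the same face at one time.

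**What to change.** - In SAP 6.3.1, delete the LOCF qualifier from the patient–clinician severity bullet.
- In SAP 6.6.3 and the introduction to 7.3, state that the comparison uses only observed ratings from both raters at the same encounter, as an exception to the general LOCF rule in 6.9. Carry this into the notes to Tables 7.3.1–7.3.4 and the corresponding figures in Section 8.9.
- Where assessment dates are held, report the median and range of days between the two ratings at each encounter. A fixed cut-off such as 4 days is not recommended: the documents do not establish that an IGA date is recorded separately from the form entry, and a filter on entry dates could drop valid same-visit pairs.
- SAP 6.6.5 needs no change, since it already rules out imputation for the caregiver–patient comparisons.

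The cost is a few lines of SAP text and, if dates exist, one derived variable. The Week 4 and Week 8 columns will have slightly fewer subjects.

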### **6.3.1 *Summary Statistics***

The descriptive statistics for all the continuous variables will include the mean, median, standard deviation (SD), minimum, maximum, and number of Subjects. Descriptive summaries will be provided for raw, and CFB values for relevant endpoints, where applicable. Frequency distributions for all the categorical variables will be presented as counts and percentages. Summaries will be provided by encounters (Baseline, Week-12, and Weeks 4/8 where appropriate). Results from the descriptive analyses will be presented as summary tables and figures.

### **6.3.2 *Subgroup Analysis***

Primary and select additional outcome measures (as individually identified in the following sections) will be summarized and repeated for the following subgroups, using FAS:

- Gender: male and female
- Age groups: 9 to 17 years and  $\geq 18$  years
- Race: white, african-american/black, other

- Body mass index: < 25 kg/m^2 and ≥ 25 kg/m^2
- Baseline facial IGA score: moderate and severe
- Concomitant use of contraceptives in females: yes and no

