### **3.1 Subject Inclusion Criteria**

**Patient Inclusion Criteria:** In order to be eligible to participate in this study, an individual must meet all of the following criteria:

- Male or female, aged 9 years and above at the time of study recruitment.
- Has facial non-nodular AV with IGA score of moderate (3) or severe (4).
- Considered as a potential candidate for sarecycline treatment to manage their AV, per clinician's judgment.
- Able to read and write English.
- Provide consent (in case of adult patients) or assent (in case of pediatric patients) to participate in the study.
- Willing to comply with all study procedures and be available for the duration of the study.

**Caregiver Inclusion Criteria:** In order to be eligible to participate in this study, an individual must meet all of the following criteria:

- Male or female, aged 18 years and above.
- Able to read and write English.
- Primary caregiver of the study-eligible patient.
- Provide consent to participate in the study.
- Willing to comply with all study procedures and be available for the duration of the study.

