## 6 STATISTICAL CONSIDERATIONS

### 6.1 Sample Size Considerations

No formal sample size and power calculations were undertaken. Considering the descriptive nature of the study and the feasibility of recruiting the study population, approximately 300 study Subjects from across a maximum of 40 clinical sites for the entire study has been identified as a sample to guide the planned analysis addressing the study objectives. It is expected that there will be Subject attrition during the course of the study.

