## 6.3 General Statistical Procedures

### 6.3.1 Overview

Data from Site Investigators and study Subjects will be treated separately, and combined into one dataset, based on the study assessments of interest. Validated instruments will be scored according to developer guidelines, reporting domain scores and overall summary scores, as appropriate. Home-grown questions/items will be analyzed and reported individually, based on the respective response scales. Change from Baseline (CFB) in scores (for continuous variables) or proportions (for discrete variables) will be computed as Week-12 minus Baseline measure for respective question responses.

Discrete measures will be assessed using summary statistics encompassing percentage of Subjects reporting particular outcome measures. The statistical differences in discrete variables to compare different patient groups (for subgroup analysis) for a given measure at a particular timepoint (such as Baseline or Week-12), or CFB in proportion of patients reporting a particular response to an outcome measure at a particular timepoint (such as Week-12) will be assessed using a  $\chi^2$  test. In case of likert scales, to compute P-values for CFB in proportions, the top-two response categories (of a likert scale) for a given question at Baseline will be grouped together into a single group proportion (versus the rest of the population/responders all together) and compared to the same group proportion at Week-12; the procedure will be repeated for the bottom-two response categories (of a likert scale) for a given question, by grouping them together into a single group proportion and compare it to the same group proportion at Week-12. For example, for ASIS item # 1 (how oily is your face right now), proportion of patients reporting “Not at all/A little” at Baseline will be grouped together (vs. rest of the population/responders) and compared to proportion of patients reporting “Not at all/A little” at Week-12; similarly, proportion of patients reporting “Quite a bit/Very” at Baseline will be grouped together and compared to proportion of

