**Table 7.2.3. Patient Clinical Characteristics from Medical Chart**

Character	Baseline (N=x)
M1B: Gender	
Male	n (%)
Female	n (%)
M2: Primary Health Insurance	
Private health insurance	n (%)
Medicaid	n (%)
Medicare	n (%)
Uninsured	n (%)
Other	n (%)
Not available	n (%)
M3r1. Height (in inches)	N, Mean (SD), Median, Min, Max
M3r2. Weight (in lbs/pound)	N, Mean (SD), Median, Min, Max
M5: Waist circumference (in inches)	N, Mean (SD), Median, Min, Max
Body Mass Index (BMI - calculated)	N, Mean (SD), Median, Min, Max
M6: Blood pressure (in mm HG)	
M6r2. Systolic	N, Mean (SD), Median, Min, Max
M6r3. Diastolic	N, Mean (SD), Median, Min, Max
M7: Concomitant (comorbid) conditions	
M7r1. Anxiety	n (%)
M7r2. Anemia or other blood disease	n (%)
M7r3. Asthma	n (%)
M7r4. Atopic dermatitis	n (%)
M7r5. Cancer (of any type)	n (%)
M7r6. Crohn's disease / IBD	n (%)
M7r7. Diabetes	n (%)
M7r8. Depression	n (%)
M7r9. Dyslipidemia/Hyperlipidemia	n (%)
M7r10. Gastroesophageal reflux disease	n (%)
M7r11. Heart disease	n (%)

---

M7r12. Hypertension	n (%)
M7r13. Kidney disease	n (%)
M7r14. Liver damage or disease	n (%)
M7r15. Lung disease	n (%)
M7r16. Osteoarthritis, degenerative arthritis	n (%)
M7r17. Other gastrointestinal disease	n (%)
M7r18. Other	n (%)
M7r18oe A, B, C	n (%)

---

Note: Data from Clinician DCF; X patients had missing data; The denominator for the percentage is the number of patients with available data (N=X)

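### One BMI cut of 25 kg/m² for a cohort from age 9, compared without age adjustment, means the exploratory BMI subgroup comparisons may partly reflect age

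*SAP*

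**What the plan says.** SAP 3.1 admits patients "Male or female, aged 9 years and above at the time of study recruitment", with no upper limit. SAP 6.3.2 lists six one-way subgroups. One is "Body mass index: < 25 kg/m 2 and ≥ 25 kg/m 2". Age is a separate entry, beginning "Age groups: 9 to 17 years and" with 18 years or older as the other group; it is not crossed with BMI. The BMI variable in Table 7.2.3 is entered as "Body Mass Index (BMI - calculated"), next to chart height and weight. No percentile, z-score or adult-only restriction appears anywhere. Protocol 12.3.2 has the same split.

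SAP 6.3.1 sets the tests. For continuous measures, "independent sample t-tests will be used to assess statistical differences between different patient groups (for subgroup analysis"). For categorical measures, a chi-square test is used; the sentence begins "The statistical differences in discrete variables to compare different patient groups (for subgroup analysis"). Neither adjusts for anything. The same section limits their status: "Computation of statistical differences will be performed only as an exploratory step (and not for hypothesis testing"), with 0.05 as the nominal threshold.

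The BMI rows and a p-value line recur in Tables 7.1.7.1 to 7.1.7.11 (EPQ), 7.1.11 (ASIS domains), 7.1.16.1 and 7.1.16.2 (ASIS items 9 and 10), 7.2.4.5 (IGA), 7.2.4.8 (IGA success) and 7.2.9 (investigator satisfaction). Protocol 12.3.3 foresees multivariate analyses of change from baseline that adjust for baseline characteristics, where feasible. The SAP has no corresponding section or table.

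**The concern.** SAP 6.4 and 6.5 say the subgroup tables are there to explore how the PRO items and IGA success relate to subject characteristics. For BMI that requires the two rows to differ in BMI and not systematically in something else. With one fixed value applied from age 9 into adulthood, a short child has to be very heavy for that height to enter the upper row. If minors and adults reach 25 kg/m² in different proportions, the two rows differ in age mix, and any outcome that varies with age will differ between them whether or not BMI matters.

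The documents themselves treat age as relevant. They stratify by it, and SAP section 4 has caregivers complete the PROs as proxies for patients aged 9-11, so even the mode of measurement changes with age. What is at stake is any statement about BMI and effectiveness or quality of life drawn from these tables: it could be produced, or hidden, by age.

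**Working it through.** The plan states no figure to reproduce: SAP 6.1 gives no power calculation, only "approximately 300 study Subjects from across a maximum of 40 clinical sites".

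**1. What the cut means at small body sizes.** BMI = weight / height², so the weight at which BMI reaches 25 is 25 × height².
- Assumed height 135 cm: 25 × 1.35² = 45.6 kg.
- Using the 33-54 kg weight band in protocol section 5 purely for arithmetic: height = √(weight/25), so 33 kg reaches the cut only at 1.15 m or shorter, and 54 kg only at 1.47 m or shorter.

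**2. Age mix of the two rows.** Let s be the share of minors, a the share of minors at 25 or above, and b the share of adults at 25 or above. All three are assumptions.
- Minors in the lower row: s(1−a) / [s(1−a) + (1−s)(1−b)]
- Minors in the upper row: sa / [sa + (1−s)b]

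With s = 40%, a = 12%, b = 45%:
- Lower row: 0.352 / (0.352 + 0.330) = 0.352/0.682 = 51.6%
- Upper row: 0.048 / (0.048 + 0.270) = 0.048/0.318 = 15.1%
- Difference: 36.5 percentage points

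**3. Gap in outcome from age alone.** Assume a 15-point difference between minors and adults, for example in IGA success, and no BMI effect. The gap between the BMI rows is the difference in age mix × 15 points.

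| a (minors at ≥25) | Minors in lower row | Minors in upper row | Gap |
|---|---|---|---|
| 5% | 0.38/0.71 = 53.5% | 0.02/0.29 = 6.9% | 7.0 points |
| 12% | 51.6% | 15.1% | 5.5 points |
| 25% | 0.30/0.63 = 47.6% | 0.10/0.37 = 27.0% | 3.1 points |
| 45% (= b) | 40% | 40% | 0 |

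**4. Wider assumed ranges.** With N = 300, s = 30-60%, a = 15-35% and b = 40-55%, the share of minors is 4 to 45 percentage points higher in the lower row. Taking a 50% adult outcome rate and no BMI effect:
- A 10-point age effect gives a gap of 0.4 to 4.5 points. The chance of p ≤ 0.05 in that direction is about 3-11%, against 2.5% nominal.
- A 20-point age effect gives 0.9 to 9.0 points and a chance of about 3.5-32%.

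**5. How often the comparison is printed.** EPQ 11 items × 2 visits = 22; ASIS domains 4 × 2 = 8; ASIS items 9 and 10, 2 × 4 visits = 8; IGA 4 visits = 4; IGA success 1; satisfaction 1. That is 22 + 8 + 8 + 4 + 1 + 1 = 44 BMI p-values.

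**The case against.** The strongest reply is that the documents do not show the imbalance. They report no age mix and no BMI by age. A reader might infer that children and adolescents mostly fall in the lower row, or that the BMI comparison is in substance an age comparison. The documents do not support either statement: under the assumptions above the imbalance runs from slight to large, and it vanishes if both age groups have the same share at or above the cut. That part of the reply stands, and the point can only be that age may contribute.

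It is also fair that these are exploratory tests in an unpowered descriptive study, that BMI is one of six one-way splits, that the other splits are unadjusted too, and that age appears in the same tables, so a reader can see whether an outcome varies with age. The SAP never calls the upper row overweight; it is a numeric split. All of this limits the consequence.

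It does not remove the point. Exploratory status excuses imprecision, not a grouping variable that means different things at different ages. One-way age rows do not show the age mix of the BMI rows. The protocol's possible safeguard, multivariate adjustment, was conditional on feasibility and has no counterpart in the SAP.

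Two further inferences should be resisted. Treatment compliance is not affected, because its table has no subgroup rows. And age-specific percentile classes alone would not cure the problem: if the age groups were pooled again, the rows could still differ in age.

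**Conclusion.** The concern holds in a limited form. The documents establish the single cut on raw BMI, entry from age 9, the unadjusted comparisons and the repeated p-values. It follows that age can be mixed into the BMI rows. How far it is mixed in is not known. The illustrative gap of 5.5 points, or 7.0 to 3.1 points as a goes from 5% to 25%, rests entirely on the assumed age mix, the assumed shares at or above 25 kg/m² and the assumed 15-point age effect, and would be zero with equal shares. A reader might fear for the main results; nothing here touches the overall primary or secondary estimates, which do not use the BMI split. The harm is confined to the exploratory BMI subgroup rows, from which a BMI-related statement could not safely be made as they are now planned.

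**What to change.** In SAP 6.3.2, and in the BMI rows of the subgroup tables listed above, present and test the BMI split within the two age groups that 6.3.2 already defines:
- **18 years or older:** keep the 25 kg/m² cut.
- **9-17 years:** use a sex- and age-specific BMI category, naming the reference, or omit the BMI rows.
- **Pooled comparison:** print no p-value for the fixed cut across all ages.

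Under the model above, comparing within age group makes the gap due to the minor-adult difference zero in expectation. The age-specific category is needed for minors because a fixed cut would still track age between 9 and 17.

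The cost is SAP wording, slightly more programming and smaller cells. With the assumed figures and 300 patients, the adult comparison would have 180 × 0.55 = 99 against 180 × 0.45 = 81, instead of 300 × 0.682 ≈ 205 against 300 × 0.318 ≈ 95 in the pooled one, before attrition. Height and weight come from usual-care charts (Appendix A, footnote 2), so some BMI values may be missing, and the number missing should be shown. The growth reference is not named in either document and would have to be chosen.
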